4.8.6 Safety

Safety and tolerability summaries will be presented using the SAF, unless other specified.

The following tables, required by the AZ corporate standards, will not be provided for this study because the relevant data were not planned to be collected on the eCRF.

Urinalysis, baseline versus maximum value on treatment, shift table (<<analysis set>>)
Urinalysis, treatment-emergent changes (<<analysis set>>)
QTcF and QTcF intervals, at <<last>> any observation on treatment (<<analysis set>>)
Electrocardiogram results exceeding ICH reference range boundaries (<<analysis set>>)

4.8.6.1 Adverse events

Summary tables will include TEAEs only, unless otherwise specified. That is, pre- and post-treatment AEs will not be included in the summary tables of AEs. Any AE after discontinuation of study treatment and pre-treatment AEs will be flagged in the data listings as post-treatment AEs and pre-treatment AEs, respectively.

Pre-treatment AEs are defined as AEs with start date before the first dose of study treatment.

TEAEs are defined as AEs with start date and time \geq the first dose of study treatment and \leq the last dose of study treatment + 14 days.

Post-treatment AEs are defined as AEs with start date $>$ the last dose of study treatment + 14 days.

If an AE has a missing onset date then unless the stop date of the AE indicates otherwise, this will be considered treatment emergent. Similarly, if an AE has a partial onset date, then unless the partial onset date or the stop date indicates otherwise, this will be considered a TEAE. In cases where the AE start time is missing but the AE start date is the same as the first dose of study treatment, then that AE will be considered a TEAE.

An overall summary table will be produced showing the number and percentage of subjects with at least 1 AE for each of the following categories:

- Any AE.
- Any AE with an outcome = death.
- Any AE with an outcome = death, causally related to study treatment.
- Any SAE (including events with outcome = death).
- Any AE leading to discontinuation of study treatment.
- Any AE causally related to study treatment.
- Any AE with intensity = severe.

AEs will be summarised by MedDRA SOC and MedDRA PT. For each SOC/PT, the number and percentage of subjects reporting at least one occurrence will be presented i.e., for a subject, multiple occurrences of an AE will be only counted once.

Summaries will also be done on AEs with most common frequency ($\geq 5\%$), non-serious AEs occurring in $\geq 5\%$ subjects, causally related to study treatment, outcome of death, serious AEs, SAEs causally related to study treatment, leading to discontinuation of the study treatment, and leading to discontinuation of study treatment, causally related to study treatment. Number and percentage of subjects with AEs by PT and relationship will also be provided.

A summary of the number and percentage of AEs by SOC and PT will be presented along with a separate summary of the number and percentage of SAEs by SOC and PT.

The number and percentage of subjects with AEs by SOC and PT and maximum reported intensity (mild, moderate, severe) will be summarised.

Key subject information for AEs with outcome of death will be summarised for all subjects. Similarly, key subject information for SAEs and AEs leading to discontinuation of investigational product will be summarised.

Separate listings of AEs leading to death and SAEs will be presented.

AEs with missing relatedness will be considered related and AEs with missing intensity will be considered as maximum intensity.

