6.3 Recording of adverse events

6.3.1 Time period for collection of adverse events

Adverse Events will be collected from randomisation, Visit 2 throughout the treatment period and including the follow-up period Visit 6.

SAEs will be recorded from the time of informed consent.

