3.4 Safety outcomes

3.4.1 Adverse events

Adverse events will be collected throughout the treatment period and including the follow-up period (Visit 6).

Serious AEs (SAEs) will be collected from the time of informed consent (Visit 1) whereas AEs will be collected from randomisation (Visit 2), throughout the treatment period and including the follow-up period (Visit 6).

The latest version of the Medical Dictionary for Regulatory Activities (MedDRA) dictionary will be used to code the AEs. The investigator's verbatim term for each AE will be mapped to a system organ class (SOC) and preferred term (PT) from MedDRA. All coding will be performed by the Medical Coding Team.

Treatment emergent adverse event (TEAE) is defined as an AE that started on or after treatment start date and within 14 days after treatment stop date.

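### SAP 4.8.6.1 gives an adverse event starting 1 to 14 days after discontinuation two labels, post-treatment and treatment-emergent, and the label decides whether it is tabulated

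*SAP*

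**What the plan says.** SAP 4.8.6.1 opens with a default for table content: "Summary tables will include TEAEs only, unless otherwise specified". It then spells out the consequence: "pre- and post-treatment AEs will not be included in the summary tables of AEs". The next sentence governs the listings: "Any AE after discontinuation of study treatment and pre-treatment AEs will be flagged in the data listings as post-treatment AEs and pre-treatment AEs, respectively".

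Later in the same section come the formal definitions. A treatment-emergent event may start as late as "the last dose of study treatment + 14 days", and "Post-treatment AEs are defined as AEs with start date $>$ the last dose of study treatment + 14 days". SAP 3.4.1 agrees, describing a treatment-emergent event as "an AE that started on or after treatment start date and within 14 days after treatment stop date".

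On collection, Protocol 6.3.1 states: "Adverse Events will be collected from randomisation, Visit 2 throughout the treatment period and including the follow-up period Visit 6". Serious events are recorded from consent.

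**The concern.** The flag sentence and the formal definitions use the same term, post-treatment, for different sets of events. Under the flag sentence the class begins as soon as study treatment is discontinued. Under the definitions it begins 14 days after the last dose. Because the sentence just before the flag sentence uses that term to exclude events from the tables, the conflict may reach beyond the listings. A programmer who follows the text literally could produce listing flags that disagree with the tables, or tables that omit events from the two weeks after stopping.

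Safety and tolerability is a stated objective (Protocol 2.3, SAP 1.1.3). Under the narrow meaning of discontinuation the conflict falls only on patients who stopped early, and an adverse event is one of the listed reasons for stopping (Protocol 3.9). Off-drug events could then be counted for completers and left out for those patients.

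**Working it through.** The plan gives no figure of its own on this point, so the check sets the rules side by side and then counts days.

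**Inputs**
- L, day of last dose. Visit 5 is Day 15 ± 1 (Protocol Table 1), with a dose taken at the site (Protocol 7.2), so L is 14 to 16 for a completer and earlier for a premature stopper.
- V, day of Visit 6. Table 1 gives Day 28 ± 2, so 26 to 30. Protocol 1.4 and SAP 1.2 instead describe Visit 6 as about 14 days after the last dose at Visit 5.
- Treatment-emergent limit: L + 14 (SAP 3.4.1 and 4.8.6.1).

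**One event under both rules.** Take a patient who stops prematurely with last dose on Day 8 and has an AE starting on Day 11.
- Flag sentence: the AE is after discontinuation, so it is post-treatment, a class excluded from the tables by default.
- Definitions: the limit is 8 + 14 = Day 22, and 11 ≤ 22, so it is treatment-emergent and tabulated. It is not post-treatment, because that requires a start after Day 22.

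**Days carrying two labels** = min(L + 14, V) − L.
- Narrow reading (premature stopping only): completers 0. Early stopper with L = 5, V = 28: 19 − 5 = 14. With L = 8, V = 28: 22 − 8 = 14. The maximum is 14.
- Broad reading (finishing the course also counts), nominal times L = 15, V = 28: min(29, 28) − 15 = 13 days (Days 16 to 28), and 13/28 = 46%.
- Broad reading across the visit windows: the lowest is L = 16, V = 26, giving 26 − 16 = 10 days, 10/26 = 38%. The highest share is L = 14, V = 28, giving 28 − 14 = 14 days, 14/28 = 50%.

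**After aligning the flag sentence with the definitions**, the number of days with two labels is 0 on either reading.

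**The 14-day limit, checked separately.** Days collected but past the limit = max(0, V − (L + 14)).
- Completer at nominal times: 28 − 29 < 0, so 0 days. The worst case in the windows is L = 14, V = 30: 30 − 28 = 2 days.
- Early stopper, if Visit 6 stays at Day 28:

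| Last dose day | Limit (L + 14) | Days past limit |
|---|---|---|
| 1 | 15 | 13 |
| 5 | 19 | 9 |
| 8 | 22 | 6 |
| 10 | 24 | 4 |
| 12 | 26 | 2 |

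- Early stopper, if Visit 6 is tied to last dose + 14 days: 0 days, or at most 2 if the ± 2 day window is assumed to apply to that anchor.

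**The case against.** The best defence is that the documents largely settle the matter. The flag sentence speaks of the listings. Table content follows the treatment-emergent rule, and three concordant statements (two definitions in 4.8.6.1 and one in 3.4.1) put the boundary at 14 days. On that view the likely harm is a wrong listing flag. This is fair and limits the weight of the point. It does not remove the contradiction, because one section still uses one term in two senses and attaches table exclusion to it.

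A reader might infer three stronger things that the documents do not support.

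- *That nearly half of the collection period drops out of the tables.* The 46% figure needs discontinuation to include completing treatment and the listing sentence to override the formal definitions. SAP 4.8.1 lists completing and discontinuing treatment as separate categories, which favours the narrow reading.
- *That the 14-day limit wrongly drops later events of early stoppers.* The limit is a pre-specified choice, stated consistently in two sections. Protocol 3.9.1 separates stopping drug from leaving the study but gives no visit schedule for early stoppers. The table above applies only if they are followed to calendar Day 28.
- *That serious events and deaths falling outside the window appear only in listings.* The treatment-emergent restriction applies unless otherwise specified. Section 4.8.6.1 also provides key subject information for serious events and for deaths, the latter for all subjects, in addition to the separate listings.

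The effect on a table row should not be overstated either. At the SAP's 10 patients per arm, one patient is 1/10 = 10 percentage points. Each subject is counted once per row, so an omitted event changes only a row in which that patient has no other tabulated event.

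**Conclusion.** The contradiction is real and lies within a single section. An AE starting 1 to 14 days after discontinuation is post-treatment by the flag sentence and treatment-emergent by the definitions. The extent is up to 14 days per early stopper and none for completers on the narrow reading, and 13 of 28 collection days at nominal times (10 to 14 days, 38% to 50%, across the visit windows) on the broad one. The narrow reading fits the SAP's own usage better.

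The 14-day limit is not an error in itself. Whether it drops any collected events of early stoppers depends on when Visit 6 falls for them, which the documents leave open. The documents give no count of early stoppers, so the number of events affected cannot be computed.

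**What to change.** Reword the flag sentence in SAP 4.8.6.1 so that the listings flag as post-treatment only events starting more than 14 days after the last dose, and as pre-treatment those starting before the first dose. Both flags then match the definitions that follow. Do not simply delete the sentence: it also carries the pre-treatment flag, which is needed because serious events are recorded from consent.

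Optionally, add a listing flag that separates treatment-emergent events starting on or before the last dose from those starting after it.

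Separately, reconcile the timing of Visit 6 between Protocol Table 1 (Day 28 ± 2) and the text (about 14 days after the last dose), and state what applies to a patient who stops early. Extending the tabulated period to Visit 6 for everyone would be a preference, not a correction.

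The main change costs one sentence in the SAP and a check of one programming flag. It needs no new data.

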4.8.6.2 Overdose

Details of subjects who overdosed will only be listed with details regarding actual treatment group.

4.8.6.3 Laboratory variables

Observed results and changes from baseline at each scheduled visit will be summarised for each quantitative haematology and clinical chemistry parameter. The following rules will be applied if more than one observation is available for a subject at a single visit:

- If there are two or more observations at the same scheduled visit, the observation closest to the target day will be used in the summary
- If two observations are equidistant from the target day and the ties are on different sides of the target day, the observation with the earlier assessment date will be used in the analysis.
- If two observations are equidistant from the target day and the ties located on the same sides of the target day (i.e. more than one observation for the same day but different time), the observation with the earlier (if the assessment day is equal or larger than the target day) or later (if the assessment day is smaller than the target day) assessment time will be used in the analysis.

A shift table from baseline to minimum value post-baseline will be provided for qualitative haematology and chemistry values (low, normal, high). Similarly, a shift table from baseline to maximum value post-baseline will be provided for qualitative haematology and chemistry values (low, normal, high). Low, normal and high will be defined based on Covance reference ranges.

To identify potential Hy's Law cases, a listing of subjects who have ALT or AST $\geq 3 \times$ ULN and total bilirubin $\geq 2 \times$ ULN will be presented. This listing will include all visits for this subset of subjects.

A plot will also present maximum post-baseline ALT/AST versus maximum post-baseline total bilirubin, expressed as multiples of ULN.

Line plots of the mean (+/- SE) of the following clinical chemistry and haematology parameters will be presented in a figure: CRP, glucose, potassium, ESR, haemoglobin, platelets and leukocytes.

Key subject information for haematology and chemistry results outside the Covance reference ranges will be provided, along with an overview of number and percentage of subjects with results outside the reference ranges post-baseline.

Pregnancy test results will only be listed for eligible subjects of childbearing potential.

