1.2 Rationale for study design, doses and control groups

This is a Phase 2a, randomised, double-blind, parallel arm study to assess the efficacy, safety and tolerability of 40 mg AZD9567 compared to prednisolone 20 mg in patients with active RA. According to the American College of Rheumatology Guidelines, short-term glucocorticoid treatment is indicated to control disease in RA patients with moderate to high disease activity. The current study randomizes eligible patients with established RA and

moderate to high disease activity as defined by ACR Guidelines (DAS28>3.2) to prednisolone 20 mg or AZD9567 40 mg for 14 days.

Prednisolone 20 mg is chosen as a moderate dose of prednisolone that falls within the ACR recommendations for treatment of active disease as moderate doses have been shown to be as effective as higher doses in active early RA ([ter Wee et al, 2015](#)). A two weeks duration of therapy was chosen on the basis that prior study has suggested that this duration can significantly impact disease activity as measured by DAS28 score ([Gerlag et al, 2004](#)).

A dose AZD9567 of 40 mg has been selected based on review of available safety, PK, and PD data from the first studies in humans in which AZD9567 was administered to healthy volunteers as single doses 2, 10, 20, 40, 80, 100, 125 and 155 mg (D6470C00001) and, in a multiple dose setting, once daily for 5 days using 10, 20, 40 and 80 mg. (D6470C00002). AZD9567 was well tolerated in all studied dose levels.

The selected AZD9567 dose 40 mg showed effects on inflammatory activity (reduced lipopolysaccharide (LPS) stimulated TNF_α response) and on the HPA axis (plasma cortisol reduction) similar to what was observed for 20 mg prednisolone.

Although the selected comparator dose of 20 mg prednisolone is known to be efficacious in RA and considered safe and tolerable for 14 days administration, it also has significant effect on glucose homeostasis. The 40 mg dose of AZD9567 showed a significantly better side effect profile with respect to glucose levels after an oral glucose tolerance test (OGTT) compared to prednisolone 20 mg in the ongoing MAD study (D6470C00002).

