4. STUDY PLAN AND TIMING OF PROCEDURES

Table 1 Study Plan detailing the procedures

Study procedures	Screening Visit 1	Day 1 Visit 2 (within 1 week of V1)	Day 5 Phone call Visit 3	Day 8 +/- 1 Visit 4	Day 15 +/- 1 EOT ^a Visit 5	Day 28 +/- 2 Follow-up Visit 6
Inclusion/exclusion criteria	X					
Demographic data	X					
Medical history (incl. RA history and oral health)	X					
Concomitant medication	X	X	X	X	X	X
Informed consent	X					
Informed consent for genetic sample	X					
Randomisation		X				
Study drug dispensation		X ^b		X		
Study drug administration:		X ^b	→	→ NB: at site	X NB: at site	
Study drug return					X	
Adverse events		X	→	→	→	X
Serious adverse events	X	→	→	→	→	X
Vital signs (BP/P and body temperature)	X	X ^d		X	X	X
12-lead ECG	X	X ^{d, f}			X	X
Clinical laboratory evaluations (Haematology, serum biochemistry, endocrinology ^e , and urine ^e analysis)	X ^c	X ^d		X ^d	X ^d	X
Pregnancy test (serum)	X					X
Erythrocyte sedimentation rate, ESR (at site)	X	X ^d		X ^d	X ^d	X
Physical examination,	X	X		X	X	X
Body weight & height ^e	X				X	X
DAS28-CRP	X	X ^d		X	X	X
ACR20, 50, and 70	X	X ^d		X	X	X
SJC and TJC 66/68	X	X ^d		X	X	X
Blood sampling for exploratory biomarkers (cortisol, serum)		X ^{d,g} Profile: 0, 1, 2, 3, 4 and 6 h			Pre dose ^g & 1, 2, 3, 4 and 6 h post dose	
Blood sampling for exploratory biomarkers (LPS stimulated TNF α , whole blood)		X ^d Profile: 0, 1, 2, 3, 4 and 6 h			Pre dose & 1, 2, 3, 4 and 6 h post dose	
Blood sample (whole blood) for mRNA ⁱ		X ^d			X ^h	

Table 1 Study Plan detailing the procedures

Study procedures	Screening Visit 1	Day 1 Visit 2 (within 1 week of V1)	Day 5 Phone call Visit 3	Day 8 +/- 1 Visit 4	Day 15 +/- 1 EOT ^a Visit 5	Day 28 +/- 2 Follow-up Visit 6
Blood sample for other potential biomarkers (serum)		X ^d			X ^d	X
Blood sample for DNA (future exploratory research)		X ^b				
Blood sampling for PK of AZD9567/ prednisolone					Pre-dose, 0.25, 0.5, 1, 1.5, 2, 3, 4 and 6 h	

^a End of treatment

^b After randomisation

^c Local lab

^d Pre-dose

^e Only at Visit 1

^f Only performed if Visit 1 was >3 days ago

^g Preferably starting as close to 08.00 as possible

^h At 1h post dose (C_{max})

ⁱ A peripheral blood mononuclear cell method may be used at selective site/s

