5.2 Safety assessments

5.2.1 Laboratory safety assessments

Blood and urine samples for determination of clinical chemistry, haematology, and urinalysis will be taken at the times indicated in the Study Plan (see Section 4).

Additional safety samples may be collected if clinically indicated at the discretion of the Investigator. The date, time of collection and results (values, units and reference ranges) will be recorded on the appropriate eCRF.

A central laboratory will be used in this study (Covance Central Laboratory Services) but for the safety lab panel at Visit 1 also local labs will be used. The clinical chemistry, haematology and urinalysis can therefore be analyzed at a local laboratory at or near to the Investigator site both at Visit 1 and if needed on ad hoc basis if deemed necessary by the investigator. Sample tubes and sample sizes may vary depending on laboratory method used and routine practice at the site. Reference values from all labs used in the study will be included in the eCRF.

The following laboratory variables will be measured:

Table 2 Laboratory Safety Variables

Haematology/Haemostasis (whole blood)	Clinical Chemistry (serum or plasma)
B-Haemoglobin (Hb)	S/P-Creatinine
B-Leukocyte count	S/P-Bilirubin, total
B-Leukocyte differential count (neutrophils, lymphocytes, monocytes, eosinophils and basophils)	S/P-Alkaline phosphatase (ALP)
B-Platelet count	S/P-Aspartate transaminase (AST)
Erythrocyte sedimentation rate, ESR	S/P-Alanine transaminase (ALT)
	S/P-Albumin
	S/P-Potassium
Urinalysis (dipstick)	S/P-Calcium, total
U-Hb/Erythrocytes/Blood	S/P-Sodium

U-Protein/Albumin	S/P-Creatine kinase (CK)
U-Glucose	S/P-C-reactive protein (CRP)
	S/P-Low density lipoprotein (LDL)
	S/P-High density lipoprotein (HDL)
	S/P-Free fatty acids (FFA)
Endocrinology	S/P-fasting glucose ^b
FSH ^a	S/P-insulin

^a Only at Visit 1 for women under the age of 50 considered to be post-menopausal to determine that the hormones are in the post-menopausal range

^b Fasting glucose on Visit 2, Visit 4 and Visit 5.

The Investigator should make an assessment of the available results with regard to clinically relevant abnormalities. The laboratory results should be signed and dated and retained at centre as source data for laboratory variables. For information on how AEs based on laboratory tests should be recorded and reported, see Section 6.3.

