3.2.1 ACR20, ACR50 or ACR70

Subjects will be considered to have an ACR20, ACR50 or ACR70 response if a 20%, 50% or 70% improvement from baseline (respectively) occurred. The ACR20, ACR50 or ACR70 responses will be derived at each of the following post-baseline scheduled assessments:

- Day 8, Visit 4.
- Day 15, Visit 5.
- Day 28, Visit 6.

As Day 28, Visit 6 is a follow-up visit and two week off-treatment, a possible decrease in efficacy is expected.

A subject will have an ACR20 response if all of the following occur:

- A $\geq 20\%$ improvement in the SJC 66 (Section 3.2.2 [Swollen Joint count](#)).
- A $\geq 20\%$ improvement in the TJC 68 (Section 3.2.3 [Tender Joint count](#)).
- A $\geq 20\%$ improvement in at least 3 of the following 5 assessments:
 - Subject's assessment of pain:
Obtained from the VAS score on the Health Assessment Questionnaire (HAQ) eCRF.

- Subject's global assessment of disease activity (GH):
Obtained from the VAS score on the SARA eCRF.
- Physician's global assessment of disease activity:
Derived from the VAS score on the Investigator's Global Assessment of RA (IARA).
- Subject's assessment of physical function:
As derived by the Total score on the HAQ eCRF. See Appendix A Health assessment questionnaire score derivation for more information.
- Acute phase reactant (CRP measure in mg/L).

A subject will have ACR50 or ACR70 response if a 50% or 70% improvement from baseline (respectively) rather than 20% was observed in the criteria specified above for ACR20.

Refer to Section 4.4.3 Missing ACRxx components for missing ACR components.

3.2.2 Swollen Joint count 66

The following 66 joints (33 left, 33 right) will be evaluated for swelling:

- 2 each: Temporomandibular, sternoclavicular, acromioclavicular, interphalangeal joints of the thumbs, wrist joints, elbow joints, shoulder joints, knee joints, ankle mortise and tarsus.
- 8 each: PIP joints of the fingers, distal interphalangeal joints.
- 10 each: Metatarsophalangeal, MCP joints, toe joints.

The swollen joint count represents the number of joints in which there is synovial fluid and/or soft tissue swelling, but not if bony overgrowth is found.

SJC = Sum of swollen joints with present status on eCRF. Maximum SJC = 66.

Refer to Section 4.4.2 Missing tender or swollen joints for missing joint counts.

3.2.3 Tender Joint count 68

The following 68 joints (34 left, 34 right) will be evaluated for swelling:

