3.4.4 Laboratory data

Blood and urine samples for determination of clinical chemistry, haematology, endocrinology, and urinalysis will be taken at the times indicated in the Study Plan and Timing of Procedures (refer to protocol Table 1).

The parameters to be determined are presented in Appendix C – Laboratory Parameters.

Changes from baseline in continuous laboratory variables to each post-baseline assessments will be calculated.

Observed values will be compared to the central laboratory reference ranges and all observed values falling outside these reference ranges will be flagged.

For laboratory results below or above the limit of quantification:

- Assign as equal to the limit of quantification, for example < 100 mL will be assigned as 100 mL.

The minimum and maximum values post-baseline will be derived based on reference ranges provided in the most recent Covance lab manual available at database lock (low, normal, high). A listing of normal ranges will be provided.

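### The laboratory shift and out-of-range tables take any post-baseline value, so off-treatment Visit 6 glucose, with no fasting condition, can set the maximum and dilute the on-treatment difference between arms

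*SAP*

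**What the plan says.** **Sampling.** Footnote b to protocol Table 2 (section 5.2.1) reads "Fasting glucose on Visit 2, Visit 4 and Visit 5" and is attached to glucose alone. Insulin and free fatty acids (FFA) are in the same table with no fasting note at any visit. In protocol Table 1 (section 4), the row beginning "Clinical laboratory evaluations (Haematology, serum biochemistry, endocrinology" is ticked at Visits 1, 2, 4, 5 and 6. Visits 2, 4 and 5 are marked pre-dose, Visit 1 is marked local laboratory, and Visit 6 carries no condition. Protocol Table 3 counts five chemistry samples, which matches those five visits.

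**Visit 6 is off drug.** SAP 3.2.1 states: "As Day 28, Visit 6 is a follow-up visit and two week off-treatment, a possible decrease in efficacy is expected".

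**Analysis.** SAP 4.8.6.3 has two kinds of display:

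- By visit: "Observed results and changes from baseline at each scheduled visit will be summarised for each quantitative haematology and clinical chemistry parameter". Glucose also gets a line plot of means.
- Across visits: "a shift table from baseline to maximum value post-baseline will be provided for qualitative haematology and chemistry values", with a matching table for the minimum and an overview of subjects outside the reference ranges after baseline.

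SAP 3.4.4 supplies the derivation for the second kind: "The minimum and maximum values post-baseline will be derived based on reference ranges provided in the most recent Covance lab manual". Neither section limits the extremes to on-treatment visits, attaches a fasting condition, or makes an exception for any analyte.

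**The concern.** A shift-to-maximum table is read as a summary of the worst value each subject had because of treatment. Here the worst value may come from a sample taken about two weeks after treatment ended. For glucose, that sample is also outside the visits at which fasting is specified, yet it is classed low, normal or high in the same table as the fasting values.

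This matters more for glucose than for most analytes. Protocol 1.1 lists glucose metabolism among the unwanted effects that AZD9567 is meant to separate from efficacy. Protocol 1.2 says of prednisolone 20 mg that "it also has significant effect on glucose homeostasis", and reports a better glucose profile for AZD9567 40 mg after an oral glucose tolerance test in healthy volunteers. Table 1 of this trial has no such test, so routine laboratory glucose carries much of the comparison. High values that arise off drug at similar rates in both arms pull the two arms together in the tables that take extremes.

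**Working it through.** The plan states no figure for this point, so there is nothing to reproduce. The check is which samples enter which display, followed by an illustration of size.

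**Step 1. Which displays does Visit 6 reach?**

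| Display (SAP 4.8.6.3) | Visits used | Effect of a Visit 6 value |
|---|---|---|
| Observed value and change, by visit | Each visit in its own row | Visit 6 row only; Day 8 and Day 15 rows unchanged |
| Glucose line plot | Visits not specified | Any Visit 6 point only |
| Shift to minimum or maximum | Any post-baseline value | Can set the extreme |
| Out-of-range overview | Any post-baseline value | Can add a subject to the count |

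In the first two displays, a Visit 6 glucose change may set a value that was not required to be fasting against a fasting Visit 2 baseline. In the last two, the visits cannot be told apart once the table is built.

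**Step 2. How much can the last two be diluted?** Let p be the true rate of ever being high on treatment in an arm. Let q be the rate of a high value at Visit 6, assumed equal in both arms and independent of the on-treatment result. Then:

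- rate with Visit 6 included = 1 − (1 − p)(1 − q)
- difference between arms with Visit 6 included = (p for prednisolone − p for AZD9567) × (1 − q)

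Both p and q are assumptions, because the documents give neither.

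| Assumed on-treatment rates, prednisolone v AZD9567 | q = 0 | q = 0.1 | q = 0.2 | q = 0.3 | q = 0.5 |
|---|---|---|---|---|---|
| 50% v 20% | 30 points | 27 | 24 | 21 | 15 |
| 40% v 10% | 30 points | 27 | 24 | 21 | 15 |
| 30% v 10% | 20 points | 18 | 16 | 14 | 10 |

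Worked case, 40% v 10% with q = 0.2: 1 − 0.6 × 0.8 = 52%, and 1 − 0.9 × 0.8 = 28%. The gap is 24 points, which is 30 × 0.8.

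**Step 3. In subjects.** SAP 1.3 gives 10 per group as the agreed sample size. One subject who was normal on treatment and high at Visit 6 moves that arm's rate by 1/10 = 10 points. In the worked case, the gap goes from 3 subjects (4 v 1) to an expected 2.4.

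**Step 4. Baseline.** SAP 4.1.2 takes the last non-missing assessment on or before the first dose. That is normally the pre-dose Visit 2 sample. If Visit 2 is missing, the rule falls back to the Visit 1 sample, for which no fasting requirement is stated.

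**The case against.** The strongest reply is that glucose may not be measured at Visit 6 at all. The only blood glucose listed is fasting glucose, and footnote b can be read as naming the visits at which it is run, much as footnote a confines FSH to Visit 1. This reading is tenable. The documents do not settle it, and it limits the glucose point to the case where a Visit 6 value exists.

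A second reply is that follow-up belongs in a safety display. Treatment-emergent adverse events run to 14 days after the last dose (SAP 4.8.6.1), and vital signs also use post-baseline extremes with no on-treatment limit (SAP 4.8.6.4). That is a fair account of the SAP's general approach. However, an adverse-event window does not mix sampling conditions as the glucose table may. The corporate-standard urinalysis table that SAP 4.8.6 names among those not produced is itself defined by the on-treatment maximum.

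A third reply is that SAP 4.8 plans no formal safety analysis and that the numbers are small. Both are true, but descriptive tables are then what readers will rely on.

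A reader might also infer more than the documents support:

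- **That insulin and FFA are fasting at Visits 2, 4 and 5.** Footnote b covers glucose only. They may share the same draws, but that is inference.
- **That Visit 6 is non-fasting.** The documents are silent. They only omit a requirement.
- **That Visit 6 is pooled into change from baseline.** It is not; those summaries are by visit.
- **That the metabolic comparison is masked.** The Day 8 and Day 15 summaries remain intact.
- **That these are the only metabolic data.** LDL, HDL and urine glucose are also in Table 2.

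**Conclusion.** The point holds for the minimum and maximum shift tables and for the out-of-range overview. As written, any Visit 6 chemistry value enters them, and a Visit 6 glucose value would be off drug with fasting not required. Visit 6 insulin and FFA enter by the same route, with fasting status unstated at every visit. The documents give no basis for saying in which direction those two would move.

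The difference between arms in these tables shrinks by a factor (1 − q), so by 10% to 50% for q from 0.1 to 0.5. This rests on assumed rates, on q being equal in the two arms and on independence. If the subjects high at Visit 6 are mostly those already high on treatment, the dilution is smaller. If no glucose is run at Visit 6, there is none for glucose. Should Visit 6 turn out to be fasting, off-drug values would still be mixed into an on-treatment contrast.

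This is a modest, avoidable weakness in descriptive safety tables. It does not undermine the trial's metabolic comparison as a whole.

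**What to change.** Add a short rule to SAP 4.8.6.3, with a cross-reference in 3.4.4, covering glucose, and insulin and FFA from the same draws:

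- Build the minimum and maximum shift tables and the out-of-range counts from on-treatment samples: Visits 4 and 5 plus any unscheduled sample taken on treatment.
- For glucose, use fasting samples only, with the fasting pre-dose Visit 2 sample as baseline.
- Present Visit 6 separately as off-treatment follow-up, including in the glucose line plot.
- State whether glucose is measured at Visit 6, and label the fasting status of glucose, insulin and FFA at each visit as actually collected. Do not assume that Visits 1 and 6 are non-fasting.

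The cost is a few sentences and a visit filter in the table programs, with no new data. The one loss is small: extremes seen only at follow-up leave the shift table, but they stay visible in the Visit 6 display.
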